10.2 General aspects

Statistics will be primarily descriptive and will be based on means (+/- standard deviation) or medians [minimum-maximum] depending on the distribution of quantitative variables. Qualitative variables will be described in terms of numbers and percentages. Univariate comparisons will use the usual statistical tests after verification of the distribution of the variables (Chi2 or Fisher's test, t-test, anova or their non-parametric equivalents Wilcoxon and Kruskal-Wallis tests).

The risk of low quality of life in the presence of impaired muscle function will be described by Odd-Ratios.

Tests will be performed at the 5% significance level. The 95% confidence intervals will be provided for each estimate.

Calculations will be done using SPSS v21 IBM and R software (version 3.6.1, www.R-project.org).

11 Expected results in terms of scientific and professional advances

This study will evaluate the association between peripheral muscle function and quality of life impairment in obese patients hospitalized in HDJ Nutrition.

The results of this study will confirm the association of muscle status on quality of life in obese patients, which is not yet clearly established in the scientific literature. If applicable, these results will make it possible to propose non-invasive and inexpensive predictive tools to screen for muscle damage in this patient population. This screening could make it possible to propose early management programs, such as exercise re-training or the introduction of adapted physical activity.

12 Expected benefits and risks for patients

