7.2 Standard evaluation procedures

7.2.1 Hand Grip Force

The maximum grip force of both hands will be measured with the portable hydraulic dynamometer JAMAR® (*Sammons Preston Rolyan Nottinghamshire, UK*) (**Appendix 2**). The dynamometer is adapted to each patient: adjustment of the hand allowing the flexion of the metacarpophalangeal joints. The grip force is obtained in kilograms (kg).

The evaluation protocol consists of three maximum voluntary isometric contractions to be held for 5 seconds, with a minimum rest period of 60 seconds. The highest value will be used to determine the maximum grip strength. The patient is placed in a seated position, with the back against the back of the chair and the feet flat on the floor. The arm position is standardized with the shoulder in adduction and neutral rotation, the elbow bent at 90°. The forearm is placed in a neutral position and rests on the support surface. The hand is aligned with the forearm.

Specific verbal instructions and encouragement are given to the patient.

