10.1 Calculation of the study size

Two groups of patients will be identified within our obesity patient population: a group of patients with low quality of life and a group with high quality of life. The median SF-36 quality of life score will be used to differentiate these 2 groups.

The echogenicity of the rectus femoris will be compared between these 2 groups, in order to evaluate the association between the muscular alteration of the rectus femoris by measuring echogenicity and the quality of life.

To our knowledge, no publication has evaluated the echogenicity of the rectus femoris in a population of obese patients. In the literature, an echogenicity of the rectus femoris of 120.9 ± 15.4 was found in a population of elderly patients (25). Given the presence of common pathophysiological mechanisms and similar sonographic characteristics (thickness and mCSA) in muscle damage between the elderly and obese patients, we hypothesize that the echogenicity of the rectus femoris in obese patients is similar to that in the elderly patient group with low quality of life.

In the absence of clinically relevant echogenicity difference data, we pragmatically expect a difference of at least 10 points (based on the alteration in muscle echogenicity of the resuscitation patient in 7 days (28)).

Thus, with a risk $\alpha = 0.05$ and a power of 90%, the number of subjects needed, for a two-sided test is 42 patients per group, or 84 in total.

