16.3 Appendix 3: Maximum Voluntary Force (MVF) of the quadriceps

[figure not shown]

Figure 4. Représentation schématique des conditions de réalisation de la mesure de la force maximale volontaire isométrique du quadriceps et calcul du moment de force produit. Lors de la réalisation contraction maximale volontaire du quadriceps, le patient génère une force F appliquée sur le contre-appui tibial (sangle ou dynamomètre). Le moment de force (Nm) produit par le patient vaut $F \text{ (N)} \times d \text{ (m)} \times \sin \alpha$ soit $F \text{ (N)} \times d \text{ (m)}$ avec $\sin 90^\circ = 1$. α : angle de flexion du genou (90°); d : distance du centre articulaire du genou au point d'application de la force.

Bachasson et al. Ambulatory measurement of isometric maximum voluntary quadriceps force in COPD patients, Rev Mal Respir, 2014

Predicted Quadriceps force (Nm)	
Q Right	$\text{FMV(Nm)} = 66.37 - (0.87 \times \text{age}) + (46.09 \times \text{Sex [0 if female, 1 if male]}) + (1.21 \times \text{weight (Kg)})$.
Q Left	$\text{FMV(Nm)} = 78 - (0.87 \times \text{age}) + (49.70 \times \text{Sex [0 if female, 1 if male]}) + (0.96 \times \text{weight (Kg)})$.

Hogrel. JY et al. Development of a French isometric strength normative database for adults using quantitative muscle testing. Arch Phys Med Rehabil, 2007

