16.4 Appendix 4: Muscle ultrasound procedure

A linear probe will be used for the measurements. A set of predefined settings of the gain and depth parameters will be used for all measurements.

Patient positioning

The patient is installed in dorsal decubitus (as strict as possible), with the lower limbs in extension and neutral position of rotation.

Placement of the probe

The probe is placed in contact with the skin via an ultrasound gel. The pressure exerted with the probe is perpendicular to the plane of the bed, in line with the femur and must be as low as possible to obtain a representative image of the muscle. Excessive pressure will cause deformation of the subcutaneous tissues and therefore of the muscle. There are two ways of orienting the probe: in the transverse or sagittal plane.

Measurements on the quadriceps

[figure not shown]

Figure 1

The probe is placed on the anterior aspect of the thigh, 2/3 of the way from the anterior superior iliac spine to the upper edge of the patella, plumb with the femur (**Figure 1**) (39). The muscle chiefs studied were the rectus femoris and the vastus intermedius.

[figure not shown]

Figure 2

Muscle thickness

In the transverse plane, measurement of the distance between the upper and lower fascias of the muscle body (Figure 2). It is measured directly on a frozen image. The thickness of the rectus femoris (DF) and the vastus intermedius (VI) will be measured on the right. The average of 3 measurements will be taken.

[figure not shown]

Figure 3

Cross-Sectional Area (CSA):

Still in the transverse plane, measure the cross-sectional area of the rectus femoris using the caliper to delineate the boundaries of the rectus femoris (Figure 3).

Pennation angle

Place the probe along the axis of the muscle. The angulation of the muscle fibers in relation to the underlying fascia becomes visible (pennation of the fibers (Figure 4). The angle between a muscle fiber and the underlying fascia will be measured only on the rectus femoris:

[figure not shown]

Figure 4

Echogenicity

Save the image used to measure the thickness and cross-sectional area. In the Image J software, delimit a 1 cm area² and analyze the variations of the gray levels. The software provides a histogram with a global value of the grey level going from 0 to 255 - 0 corresponding to black and 255 to white (28).

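### Section 10.2 plans odds ratios for 'impaired muscle function' without naming a measure or cut-off; an odds ratio per 1 SD of the continuous measure avoids cut-point selection and loses less information

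*Combined protocol and SAP*

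**What the plan says.** Section 10.2 (General aspects) states: "The risk of low quality of life in the presence of impaired muscle function will be described by Odd-Ratios". The same section sets a 5% significance level and promises 95% confidence intervals. It names chi-square or Fisher, t-test, ANOVA and their non-parametric equivalents, and no regression model. The synopsis does not repeat the odds-ratio sentence, but it adds that associations between categorical variables will be tested by chi-square or Fisher.

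Low quality of life is defined in section 10.1: "The median SF-36 quality of life score will be used to differentiate these 2 groups".

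Impaired muscle function is not defined. The relevant sections give raw measurements only:

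- **Echogenicity (Appendix 4):** "The software provides a histogram with a global value of the grey level going from 0 to 255". No limit is given.
- **Grip (section 7.2.1):** "The highest value will be used to determine the maximum grip strength". This is a value in kilograms, with no limit.
- **Quadriceps force (section 7.2.2 and Appendix 3):** the maximum of three manoeuvres, plus equations for predicted force by age, sex and weight. No percent-predicted limit is given.
- **Thickness and cross-sectional area (section 8.1.2 and Appendix 4):** measurement instructions only.

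**The concern.** A statement about risk in the presence of an impairment needs a yes/no exposure. Without a named measure and cut-off, several measures and many cut-offs are available once the data are seen, and the plan has no rule for choosing among them. Section 10.1 also says that rectus femoris echogenicity has not been published in obese patients, to the authors' knowledge, and that no clinically relevant difference is known. For the main measure, then, the documents supply no outside threshold.

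Two further costs arise even if a cut is fixed beforehand. Splitting a continuous measure discards information. And because the median split makes the outcome common, calling an odds ratio 'risk' invites the reader to take it as a multiple of risk. Section 11 hopes that the results may support screening tools, and an impaired/not-impaired ratio is a result that readers could use for that purpose.

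**Working it through.** **Inputs.** From section 10.1: SD 15.4, 42 patients per group, two-sided 5% level, and a difference for which "we pragmatically expect a difference of at least 10 points". Assumptions: echogenicity is normal with equal SD in both groups, and the high quality-of-life mean is 120.9 − 10 = 110.9. Only the difference matters for power.

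**The plan's own figure.** The plan gives no power or size for the odds ratios; its only figure is the 84 patients. With the stated inputs, n per group = 2 × 15.4² × (1.960 + 1.282)² / 10² ≈ 50, not 42. The stated 42 and 90% therefore do not reproduce as a two-sided calculation. That is a separate matter; 84 is used here simply as the planned number.

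**1. Power with the measure kept continuous.**
- Standard error of the difference = 15.4 × √(2/42) = 3.36.
- z = 10 / 3.36 = 2.98, and power = Φ(2.98 − 1.96) ≈ 84.5%, or 83.7% by noncentral t.
- Simulated logistic regression of low quality of life on the continuous measure gives about the same, 84%.
- The expected odds ratio per 15.4 points is exp(10/15.4) ≈ 1.91.

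**2. Power with a median cut fixed in advance.**
- Under the planning model the midpoint is 115.9. The share of the low group above it is Φ(5/15.4) = 0.627, and of the high group 0.373.
- The expected counts above the cut are 0.627 × 42 = 26.3 and 0.373 × 42 = 15.7.
- A split of 26 v 16 gives chi-square = 84 × (26² − 16²)² / 42⁴ = 4.76, which is significant. A split of 25 v 17 gives 84 × (25² − 17²)² / 42⁴ = 3.05, which is not.
- The expected table thus sits at the edge of significance. By simulation, power is about 66%.
- With no true difference, both methods have about 5% type I error.

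**3. Type I error if the cut is chosen from the data.** Simulation with no association and 42 v 42, counting studies in which at least one cut gives p<0.05 for a single measure:

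| Cuts tried | Test | Studies with p<0.05 |
|---|---|---|
| Median only, fixed in advance | chi-square | about 5% |
| Quartiles, tertiles, median | chi-square | about 13% |
| Every cut from 9 to 75 exposed | continuity-corrected chi-square | about 26% |
| Every cut from 9 to 75 exposed | uncorrected chi-square | about 42% |

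**4. Odds ratio against risk ratio.** With half the patients below the SF-36 median and half classed as exposed, p₁ = 1 − p₀, so OR = (p₁/p₀)² = RR².
- 60% v 40%: RR = 1.5, OR = 2.25.
- 70% v 30%: RR = 2.33, OR = 5.44.
- Planning model at the midpoint, 62.7% v 37.3%: RR = 1.68, OR = 2.83.

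**The case against.** A reader might infer more than the documents support, and the case against those readings is good.

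- **That the odds ratios will overstate risk.** An odds ratio is a valid measure of association, and section 10.2 names it as such. It misleads only if read as a risk ratio. What stands is that the word 'risk' invites that reading when the outcome is near 50%.
- **That the result will be driven by the cut-off.** Section 10.2 announces no search; it is silent. Under the planning model the expected odds ratio is nearly flat over central cut-offs, 2.83 to 3.29 for cuts from 100 to 130. The instability appears when a cut is picked after seeing the data.
- **That any threshold must come from these 84 patients.** This does not follow. The predicted-force equations in Appendix 3 would allow an outside definition for quadriceps strength. They come without a limit, so the gap remains.
- **That the error rate would be 42%.** This needs an exhaustive scan and an uncorrected test. Section 10.2 offers chi-square or Fisher, and a milder choice gives 13% to 26%.

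It is also fair to say that the odds ratios are peripheral. Section 10.1 compares echogenicity as a continuous measure between the two groups, none of the listed endpoints is defined as an odds ratio, and section 10.2 calls the statistics primarily descriptive. Section 11 does not tie screening tools to the odds ratios in particular. This lowers the severity. It does not supply the missing definition or recover the information lost by a split.

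**Conclusion.** The point holds as a minor one. The odds-ratio analysis implies a yes/no impairment that the plan never defines, so it is open to cut-point selection, and its label suggests risk. Even with a well-behaved fixed median cut, power falls from about 84% to about 66% under the protocol's own planning figures. If a cut were selected from the data, the type I error for one measure would be about 13% to 42%, depending on how many cuts are tried and on the test.

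The power figures rest on normality, equal SDs and a true difference of 10 points in echogenicity. The plan gives no comparable figures for grip, thickness or quadriceps force. The type I error figures apply only if selection takes place, which the documents neither announce nor rule out. The primary comparison of mean echogenicity between the two quality-of-life groups is unaffected.

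**What to change.** Replace the sentence in section 10.2 with:

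*The association of each muscle measure with low quality of life will be given as an odds ratio per 1 SD of the continuous measure (logistic regression) with 95% CI, and described as odds, not risk.*

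If a two-by-two table is also wanted, fix the measure and its cut-off before analysis and report both proportions and their difference with a 95% CI. A cut at the sample median is acceptable for that purpose, but it should be labelled above/below median. It would class half the patients as impaired by construction and does not define impairment.

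The cost is one sentence, with the same data and the same software. The downside is that the study would report no single threshold for impaired muscle function.

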12.1 Minimal risks and constraints added by the research

The risks and constraints for the patient will only be the extra time spent by the patient on the ultrasound and the quality of life assessment questionnaire. Ultrasound is a non-invasive, non-irradiating and totally painless tool.

12.2 Expected benefits for the patient

The use of non-invasive tests of muscle function could allow early identification of obese subjects whose impairment of muscle function could be associated with a poorer quality of life. This could allow us to propose an adapted therapeutic strategy, such as the implementation of an exercise training program, adapted physical activity or therapeutic education.

13 Feasibility

The patients are included in the HDJ Nutrition of the Forcilles Hospital. The whole of care, treatments, examinations and samples being carried out within the framework of their therapeutic and diagnostic management, the conditions relating to the human, material and technical means are ensured. However, if an incident were to occur, the patients would benefit from all the human and technical means of the hospital to guarantee their safety, in

accordance with the rules of hygiene and safety in force and in the respect of the integrity of the patient.

In addition, the medical and paramedical teams involved in this study have experience in clinical research, as they have already participated in other clinical trials.

Taking into account the inclusion and non-inclusion criteria, possible refusals of patients to participate in the research, potential exclusions and the recruitment experience, we estimate a minimum recruitment capacity of 50% of patients admitted to HDJ Obesity, i.e. 10 patients in 9 months.

14 Ethical and regulatory aspects

The Forcilles-Fondation Cognacq-Jay hospital promoter and the person(s) directing and supervising the research undertake that this research will be carried out in compliance with law n°2004-806 of August 9, 2004 relating to public health policy and the regulatory provisions in force (articles L.1121-1, L.1121-2 and L.1121-3 of the Public Health Code. The data recorded during this research will be subject to computerized processing in compliance with Law No. 78-17 of January 6, 1978 on information technology, files and freedoms, as amended by Law No. 2018-493 of June 20, 2018 (Decree No. 2018-687 of August 1, 2018) and Order No. 2018-1125 of December 12, 2018.

The research will be conducted in accordance with this protocol.

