6.2 Research diagram

6.3 Provisional research schedule

The duration of recruitment will be 9 months with a follow-up of patients for one day, for a total estimated duration of the study of 9 months:

- Submission to PPC: January 2022
- Start of inclusions: March 2022
- Duration of the inclusion period: 9 months
- Duration of participation of each patient: 1 day
- End of inclusions: January 2023
- Total duration of the research: 9 months
- Communication in congresses: Scientific days of the AFERO, other scientific congresses
- Publication: international journal with review committee.

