7.1 Description of the usual course of care

A total of 4 patients are admitted every Monday of the week and the last Thursday of the month. Patients are hospitalized for one day. The day begins with the reception of the patient by the nurse and continues with :

- A dietary consultation;
- A psychological consultation;
- Medical consultation;
- A consultation by the physiotherapist;
- A cardiological consultation.

After the various consultations, a summary meeting is held with the doctor, nurse, physiotherapist, psychologist and dietician. This meeting allows us to define the therapeutic strategy that will be proposed to the patient.

At the end of this meeting, the nurse receives the patient in consultation and informs him of the therapeutic proposals. Finally, the patient is received by the doctor in charge who gives him the hospitalization report. All the examinations and consultations are carried out within the usual framework of the HDJ Nutrition and are systematically prescribed by the doctor in charge.

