9.1 Pre-inclusion visit

9.1.1 Verification of inclusion and non-inclusion criteria

At the time of admission of a patient in HDJ obesity, one of the investigators of the study verifies the presence of the inclusion criteria and the absence of the non-inclusion criteria in the computerized file of the patient.

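### Does the recruitment figure of 10 patients in 9 months, with an end date that overruns the 9-month period, undermine the target of 84?

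*Combined protocol and SAP*

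**What the plan says.** Section 13 (Feasibility) gives the recruitment estimate: "we estimate a minimum recruitment capacity of 50% of patients admitted to HDJ Obesity, i.e. 10 patients in 9 months". It says this allows for eligibility, refusals, possible exclusions and past recruitment experience, and it places the study in one unit: "The patients are included in the HDJ Nutrition of the Forcilles Hospital".

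Section 7.1 describes the flow through that unit: "A total of 4 patients are admitted every Monday of the week and the last Thursday of the month". Each stay lasts one day. Section 5.5 says recruitment is consecutive.

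The target in section 10.1 is "42 patients per group, or 84 in total", and the synopsis names one centre.

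The timetable in section 6.3 reads "Start of inclusions: March 2022", "Duration of the inclusion period: 9 months" and "End of inclusions: January 2023". Each patient takes part for one day, and the total duration is also given as nine months.

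**The concern.** Section 13 joins a percentage and a count as if they were the same thing, and they are not. If 10 patients were half of all admissions, the unit would admit 20 patients in nine months, which section 7.1 reaches in five admission days. Ten is also far below the 84 required. A reader who takes the sentence at face value would conclude that the study cannot recruit its sample at a single centre in the stated time.

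The timetable adds to the doubt. Nine months from any day in March 2022 ends before January 2023, so start, length and end do not agree. If recruitment really were marginal, the study could close short of its target and lose the power on which section 10.1 rests.

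**Working it through.** **Inputs.** Four patients per admission day, on Mondays and the last Thursday of each month (section 7.1; four on each day, Thursdays included, is a reading of that sentence). Uptake 50% (section 13). Target 84 (section 10.1). Start March 2022, nine months (section 6.3).

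**The plan's own figure.** 10 / 0.50 = 20 admissions, and 20 / 4 = 5 admission days. Ten is 10 / 84 = 12% of the target. At 10 per nine months, 84 patients would take 84 / (10 / 9) = 75.6 months. The figure cannot be reproduced from section 7.1.

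**Calendar count.** Expected inclusions = admission days × 4 × 0.50.

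| Window | Mondays + last Thursdays | Admissions | At 50% |
|---|---|---|---|
| 1 Mar to 30 Nov 2022 | 39 + 9 = 48 | 192 | 96 |
| 31 Mar to 30 Dec 2022 | 39 + 10 = 49 | 196 | 98 |
| 1 Mar to 31 Dec 2022 | 43 + 10 = 53 | 212 | 106 |
| 1 Mar 2022 to 31 Jan 2023 | 48 + 11 = 59 | 236 | 118 |

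For the first window, 10 / 192 = 5.2% of admissions, not 50%. The monthly rate is 96 / 9 = 10.7, so 84 would be reached in 84 / 10.67 = 7.9 months. The uptake needed is 84 / 192 = 43.75%.

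**Likely source of the slip.** Ten per month gives 10 × 9 = 90, close to 96. The documents do not confirm this, but it is the reading nearest to section 7.1.

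**Sensitivity.** Each lost admission day costs 4 × 0.50 = 2 inclusions. Six lost days leave 42 × 2 = 84, and seven leave 82. Mondays alone give 39 × 2 = 78 by 30 November and 43 × 2 = 86 by 31 December.

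**Dates.** A 1 March start ends on 30 November, two months before 31 January 2023. A 31 March start ends at the close of December, as little as one day before January. The nine-month total is consistent with nine months of inclusion, because participation lasts one day. Only the end date is out of line.

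**Direction of the date mismatch.** The 96 already uses the earliest end date. Every other window in the table gives more, so the mismatch can widen the margin over 84 but cannot shrink it.

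**The case for a change.** The strongest case for acting is that the error is certain and the intended number is not. The margin over 84 is 12 if the figure should be 96, 6 if it should be 90, and negative at 10. Six closed days use up the 12 at 50% uptake, and Mondays alone fall short at 78. The protocol mentions neither closures nor repeat attenders. A different, smaller unit does not explain the 10: section 9.1.1 writes "At the time of admission of a patient in HDJ obesity" about the same admissions that section 13 places in the HDJ Nutrition. On this view an ethics committee cannot confirm from section 13 that the sample is reachable.

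The contradiction itself stands. The consequences drawn from it do not. Section 13 is not the only support for recruitment: the admission pattern in section 7.1, consecutive recruitment in section 5.5 and the 50% uptake together give the 96 without using the 10. The 50% is stated as a minimum, so 96 is no ceiling. An explicit allowance for closures and repeat attenders would be a preference about presentation.

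The margin also depends on 84 being the right target. With a difference of 10 and an SD of 15.4 (section 10.1), a two-sided 5% test at 90% power needs 50 per group by the normal formula (51 by the t-test), so 100 to 102 in total, which is above 96. That is a question about the sample-size calculation. Correcting the 10 would not touch it.

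**Conclusion.** Section 13 contains a clerical slip and section 6.3 a loose provisional date. Neither calls for a change to the plan. The stated 10 should be of the order of 90 to 96. The 96 assumes four new patients on every Monday and last Thursday, no closures, and one unit under two names; Mondays alone would give 78 in nine months. Against 84, the 96 leaves a margin of 12.

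No sample size, endpoint, analysis or stopping rule takes the 10 or the end date as an input. Section 6.3 presents its timetable as provisional. Each patient is measured on a single day with no follow-up, so slower recruitment would cost calendar time without altering what is measured or how it is compared. The overrun of one day to about two months adds expected inclusions. Correcting the wording would make the text tidier, but it would not change what the trial does or concludes.
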